4.4 Eligibility/screening of subjects

If potential subjects will be asked eligibility questions before obtaining informed consent, describe the process. Add the script documents and a list of the eligibility questions that will be used to your study in CATS IRB (<http://irb.psu.edu>) on the “Consent Forms and Recruitment Materials” page.

StudyFinder: If you intend to use StudyFinder (<http://studyfinder.psu.edu>) for recruitment purposes, any scripts (phone, email, or other) used when contacting StudyFinder participants as well as any eligibility screening questions must be added to your study in CATS IRB (<http://irb.psu.edu>) on the “Consent Forms and Recruitment Materials” page.

An interview using the phone questionnaire assesses likelihood of eligibility before obtaining informed consent. Subjects are informed that the information they provide is kept confidential. The data from individuals who qualify or do not qualify are kept and stored until the end of the study, then destroyed. Permission to maintain the information for subjects who qualify and contact them for future studies is requested. See Screening under “Study Design and Procedures” for screening information.

5.0 Consent Process and Documentation

Refer to “SOP: Informed Consent Process for Research (HRP-090)”, for information about the process of obtaining informed consent from subjects. HRP-090 can be accessed by clicking the Library link in CATS IRB (<http://irb.psu.edu>).

5.1 Consent Process

5.1.1 Obtaining Informed Consent

5.1.1.1 Timing and Location of Consent

Describe where and when the consent process will take place.

We obtain a consent via telephone for the subject to fast before coming to the lab for the screening.

The subject reports to Noll lab for the consenting process. The subject signs an informed consent before any screening procedures are performed.

5.1.1.2 Coercion or Undue Influence during Consent

Describe the steps that will be taken to minimize the possibility of coercion or undue influence in the consent process.

Subjects are informed throughout the study that their participation is voluntary, and they may discontinue their participation at any time. It is possible that a person enrolled in the study could be a student or employee. They are advised that participation in the study is voluntary and no aspect of their participation or non-participation has an effect on their class, grade, employment, or salary. Subjects are informed that participation or withdrawal from the study does not affect the quality of their medical care, payment or enrollment in health plans, or affect eligibility for benefits.

5.1.2 Waiver or alteration of the informed consent requirement

If you are requesting a waiver or alteration of consent (consent will not be obtained, required information will not be disclosed, or the research involves deception), describe the rationale for the request in this section. If the alteration is because of deception or incomplete disclosure, explain whether and how subjects will be debriefed. Add any debriefing materials or document(s) to your study in CATS IRB (<http://irb.psu.edu>) on the “Supporting Documents” page. NOTE: Review the “CHECKLIST: Waiver or Alteration of Consent Process (HRP-410)” to

ensure you have provided sufficient information for the IRB to make these determinations. HRP-410 can be accessed by clicking the Library link in CATS IRB (<http://irb.psu.edu>).

Subject may arrive to consenting-session fasted if subject wishes to give informed consent and have the medical screening on the same day.

5.2 Consent Documentation

5.2.1 Written Documentation of Consent

Refer to "SOP: Written Documentation of Consent (HRP-091)" for information about the process to document the informed consent process in writing. HRP-091 can be accessed by clicking the Library link in CATS IRB (<http://irb.psu.edu>).

If you will document consent in writing, describe how consent of the subject will be documented in writing. Add the consent document(s) to your study in CATS IRB (<http://irb.psu.edu>) on the "Consent Forms and Recruitment Materials" page. Links to Penn State's consent templates are available in the same location where they are uploaded and their use is required.

The potential subject signs the informed consent. A copy of the signed consent is given to the subject.

5.2.2 Waiver of Documentation of Consent (Implied consent, Verbal consent, etc.)

If you will obtain consent (verbal or implied), but not document consent in writing, describe how consent will be obtained. Add the consent script(s) and/or information sheet(s) to your study in CATS IRB (<http://irb.psu.edu>) on the "Consent Forms and Recruitment Materials" page. Links to Penn State's consent templates are available in the same location where they are uploaded and their use is required. Review "CHECKLIST: Waiver of Written Documentation of Consent (HRP-411)" to ensure that you have provided sufficient information. HRP-411 can be accessed by clicking the Library link in CATS IRB (<http://irb.psu.edu>).

If your research presents no more than minimal risk of harm to subjects and involves no procedures for which written documentation of consent is normally required outside of the research context, the IRB will generally waive the requirement to obtain written documentation of consent.

- i. The written script of the information will be provided orally (if verbal consent is to be obtained) and will include all required elements of consent disclosure.
- ii. The research presents no more than minimal risk of harm to subjects (this is for the screening fasting procedure only)
- iii. The research involves no procedures for which written consent is normally required outside of the research context.
- iv. Written information describing the research is to be provided to the subject (option to print the consent form for their records).

5.3 Consent – Other Considerations

5.3.1 Non-English Speaking Subjects

Indicate what language(s) other than English are understood by prospective subjects or representatives.

If subjects who do not speak English will be enrolled, describe the process to ensure that the oral and written information provided to those subjects will be in that language. Indicate the language that will be used by those obtaining consent.

Indicate whether the consent process will be documented in writing with the long form of the consent documentation or with the short form of the consent documentation. Review the "SOP: Written Documentation of Consent (HRP-091)" and the "Investigator Manual (HRP-103)"

to ensure that you have provided sufficient information. HRP-091 and HRP-103 can be accessed by clicking the Library link in CATS IRB (<http://irb.psu.edu>).

Not Applicable

5.3.2 Cognitively Impaired Adults

Refer to "CHECKLIST: Cognitively Impaired Adults (HRP-417)" for information about research involving cognitively impaired adults as subjects. HRP-417 can be accessed by clicking the Library link in CATS IRB (<http://irb.psu.edu>).

5.3.2.1 Capability of Providing Consent

Describe the process to determine whether an individual is capable of consent.

Not Applicable

5.3.2.2 Adults Unable To Consent

Describe whether and how informed consent will be obtained from the legally authorized representative. Describe who will be allowed to provide informed consent. Describe the process used to determine these individual's authority to consent to research.

For research conducted in the state, review "SOP: Legally Authorized Representatives, Children and Guardians (HRP-013)" to be aware of which individuals in the state meet the definition of "legally authorized representative". HRP-013 can be accessed by clicking the Library link in CATS IRB (<http://irb.psu.edu>).

For research conducted outside of the state, provide information that describes which individuals are authorized under applicable law to consent on behalf of a prospective subject to their participation in the procedure(s) involved in this research. One method of obtaining this information is to have a legal counsel or authority review your protocol along with the definition of "children" in "SOP: Legally Authorized Representatives, Children, and Guardians (HRP-013)." HRP-013 can be accessed by clicking the Library link in CATS IRB (<http://irb.psu.edu>).

Not Applicable

5.3.2.3 Assent of Adults Unable to Consent

Describe the process for assent of the subjects. Indicate whether assent will be required of all, some or none of the subjects. If some, indicate which subjects will be required to assent and which will not.

If assent will not be obtained from some or all subjects, provide an explanation of why not.

Describe whether assent of the subjects will be documented and the process to document assent. The IRB allows the person obtaining assent to document assent on the consent document and does not routinely require assent documents and does not routinely require subjects to sign assent documents.

Not Applicable

5.3.3 Subjects who are not yet adults (infants, children, teenagers)

5.3.3.1 Parental Permission

Describe whether and how parental permission will be obtained. If permission will be obtained from individuals other than parents, describe who will be allowed to provide permission. Describe the process used to determine these individual's authority to consent to each child's general medical care.

For research conducted in the state, review "SOP: Legally Authorized Representatives, Children and Guardians (HRP-013)" to be aware of which

individuals in the state meet the definition of "children". HRP-013 can be accessed by clicking the Library link in CATS IRB (<http://irb.psu.edu>).

For research conducted outside of the state, provide information that describes which persons have not attained the legal age for consent to treatments or procedures involved in the research, under the applicable law of the jurisdiction in which research will be conducted. One method of obtaining this information is to have a legal counsel or authority review your protocol along with the definition of "children" in "SOP: Legally Authorized Representatives, Children, and Guardians (HRP-013)." HRP-013 can be accessed by clicking the Library link in CATS IRB (<http://irb.psu.edu>).

Not Applicable

5.3.3.2 Assent of subjects who are not yet adults

Indicate whether assent will be obtained from all, some, or none of the children. If assent will be obtained from some children, indicate which children will be required to assent. When assent of children is obtained describe whether and how it will be documented.

Not Applicable

6.0 HIPAA Research Authorization and/or Waiver or Alteration of Authorization

This section is about the access, use or disclosure of Protected Health Information (PHI). PHI is individually identifiable health information (i.e., health information containing one or more 18 identifiers) that is transmitted or maintained in any form or medium by a Covered Entity or its Business Associate. A Covered Entity is a health plan, a health care clearinghouse or health care provider who transmits health information in electronic form. See the "Investigator Manual (HRP-103)" for a list of the 18 identifiers. HRP-103 can be accessed by clicking the Library link in CATS IRB (<http://irb.psu.edu>).

If requesting a waiver/alteration of HIPAA authorization, complete sections 6.2 and 6.3 in addition to section 6.1. The Privacy Rule permits waivers (or alterations) of authorization if the research meets certain conditions. Include only information that will be accessed with the waiver/alteration.

6.1 Authorization and/or Waiver or Alteration of Authorization for the Uses and Disclosures of PHI

Check all that apply:

- Not applicable, no identifiable protected health information (PHI) is accessed, used or disclosed in this study.** *[Mark all parts of sections 6.2 and 6.3 as not applicable]*
- Authorization will be obtained and documented as part of the consent process.** *[If this is the only box checked, mark sections 6.2 and 6.3 as not applicable]*
- Partial waiver is requested for recruitment purposes only (Check this box if patients' medical records will be accessed to determine eligibility before consent/authorization has been obtained).** *[Complete all parts of sections 6.2 and 6.3]*
- Full waiver is requested for entire research study (e.g., medical record review studies).** *[Complete all parts of sections 6.2 and 6.3]*
- Alteration is requested to waive requirement for written documentation of authorization (verbal authorization will be obtained).** *[Complete all parts of sections 6.2 and 6.3]*

6.2 Waiver or Alteration of Authorization for the Uses and Disclosures of PHI

6.2.1 Access, use or disclosure of PHI representing no more than a minimal risk to the privacy of the individual

6.2.1.1 Plan to protect PHI from improper use or disclosure

Include the following statement as written – DO NOT ALTER OR DELETE unless this section is not applicable because the research does not involve a waiver of authorization. If the section is not applicable, remove the statement and indicate as not applicable.

Not Applicable

6.2.1.2 Plan to destroy identifiers or a justification for retaining identifiers

Describe the plan to destroy the identifiers at the earliest opportunity consistent with the conduct of the research. Include when and how identifiers will be destroyed. If identifiers will be retained, provide the legal, health or research justification for retaining the identifiers.

Not Applicable

6.2.2 Explanation for why the research could not practically be conducted without access to and use of PHI

Provide an explanation for why the research could not practically be conducted without access to and use of PHI.

Not Applicable

6.2.3 Explanation for why the research could not practically be conducted without the waiver or alteration of authorization

Provide an explanation for why the research could not practically be conducted without the waiver or alteration of authorization.

Not Applicable

6.3 Waiver or alteration of authorization statements of agreement

By submitting this study for review with a waiver of authorization, you agree to the following statement – DO NOT ALTER OR DELETE unless this section is not applicable because the research does not involve a waiver or alteration of authorization. If the section is not applicable, remove the statement and indicate as not applicable.

Not Applicable

7.0 Study Design and Procedures

7.1 Study Design

Describe the type/design of trial to be conducted (e.g., double-blind, placebo controlled, parallel design, etc.). Provide a schematic diagram of study design, procedures and stages, if appropriate.

Two groups of women complete this study: 1) healthy women between the ages of 18 and 45 years (Controls); 2) women between the ages of 18 and 45 years with endometriosis. Each subject participates in a cutaneous microdialysis (MD) experiment before and after 6-9 days of oral atorvastatin (Lipitor) therapy (10mg/day). Each MD experiment includes a blood draw (e.g. miRNA, soluble LOX receptor, OxLDL, IL6, IL17, TNF α). The microdialysis experiments combine an acetylcholine dose response, perfusion of investigational agents, and local heating of the skin to explore the role of microRNA (miRNA) activation of LOX-1 receptor mechanisms in endothelial dysfunction associated with endometriosis.

7.2 Study Procedures

Provide a description of all research procedures being performed and when they are being performed (broken out by visit, if applicable), including procedures being performed to monitor subjects for safety or minimize risks. Include any long-term follow-up procedures and data collection, if applicable.

Describe where or how you will be obtaining information about subjects (e.g., medical records, school records, surveys, interview questions, focus group topics, audio or video recordings, data collection forms, and collection of specimens through invasive or non-invasive procedures to include the amount to be collected and how often). Add any data collection instruments that will be seen by subjects to your study in CATS IRB (<http://irb.psu.edu>) in the “Supporting Documents” page.

7.2.1 EXAMPLE: Visit 1 or Day 1 or Pre-test, etc. (format accordingly)

Provide a description as defined above and format accordingly.

Screening

1. The participants drink only water and do not eat for 12 hours before the screening.
2. The research nurse conducts the screening that includes pregnancy test for women who are not post-menopausal, 12-lead resting ECG, heart rate (HR), blood pressure (BP), height, waist circumference, weight, health history, creatine phosphokinase (CPK), and standard venipuncture to obtain blood (30 ml, 2 Tbsp) for complete blood count (CBC), chemistry analysis, lipid profile, protein kinase, and other substances of interest.
3. If participant takes thyroid medication, the nurse obtains thyroid stimulating hormone (TSH) level from participant. If TSH level is not available and/or has not been measured within 6 months, TSH is also measured from the blood sample.
4. We do not perform genetic analyses on the blood nor look for presence of disease (e.g. HIV).
5. We give subjects a note that informs her/his physician that the subject takes Lipitor as part of this study.

If the research nurse is unavailable for an extended period, the Clinical Research Center CRC staff performs her screening tasks. The CRC uses their admission form to admit potential participants for screening at the CRC.

7.2.2 EXAMPLE: Visit 2 or Day 2 or Post-test, etc. (format accordingly)

Provide a description as defined above and format accordingly.

Note: Subjects perform a pre- and post-statin therapy experiment.

1. Preparation for experiments
 - a. We give printed and verbal instructions outlining what the subjects need to do before they come to the lab.
 - b. Subjects continue with their normal diet except:
 - i. They refrain from consuming alcohol and caffeine (ex. coffee, tea, Coca Cola, chocolate) for 12 hours before the experiment.
 - c. On the day of the experiment,
 - i. Subjects refrain from activity that causes them to exert themselves more than a leisurely walk.
 - ii. We measure HR, BP, and oral temperature. Women who are not postmenopausal undergo a urine pregnancy test if they have not been tested within 2 weeks.
 - iii. The nurse draws 10 ml blood for analysis of relevant substances of interest such as miRNA, soluble LOX receptor, OxLDL, IL6, IL17, and TNF α .
 - iv. Microdialysis probe insertion: The subject washes the ventral forearm with antimicrobial soap. We place a tight band around the arm so we can visualize veins. For each MD site, we make pairs of pen-marks on the arm 2.5 cm (1 inch) apart and away from veins. We remove the tight band. The MD tubing enters and exits the skin at the marks. We clean the arm with povidone iodine and alcohol. We place an ice bag on the arm for 5 minutes to numb the skin. Then we insert a thin needle into the skin at each entry mark. The needle's tip travels between the layers of skin for 2.5 cm (1 inch) and leaves the skin at the matching exit mark. We thread the MD tubing through the needle. Next, we withdraw the needle leaving the tubing in the skin. Any redness of the skin subsides in about 60 – 120 minutes.
 - v. We initiate lactated Ringer's perfusion in all MD probes at 2 μ l/min.
 - vi. We attach 3 ECG leads to measure heart rate, and place a cuff on the upper arm sans the MD probes to measure blood pressure. We place a local skin heater and laser Doppler probe over each MD site. We measure heart rate, local temperature, and skin blood flow (SkBF) throughout the MD experiments. We also measure blood pressure every 5-7 minutes (brachial osculation and/or critical care monitor).
2. MD Experiment – Pre-Statin Therapy

a. Acetylcholine (ACh) Dose Response

We prepare 5 MD sites: Probe 1. Lactated Ringer's only (control)

Probe 2. Lactated Ringer's + LNAME

Probe 3. Lactated Ringer's + Poly I:C

Probe 4. Lactated Ringer's + atorvastatin

Probe 5. Lactated Ringer's + (LNAME + Poly I:C) or (LNAME + atorvastatin)*

*Note: Pilot experiments lead to development of the final protocol. Two treatments are explored at MD Probe 5 during pilot experiments. Pilot experiments also determine final doses of investigational agents.

We clamp the temperatures of the local heaters at 34°C (93°F). We add Poly I:C or atorvastatin to probes 3, 4, and 5 as indicated above. After 30 minutes, we add LNAME to Probes 2 and 5. Twenty minutes later, we record a 10-minute baseline. After the baseline, we add the first concentration of ACh to the perfusate at each probe. Each site receives 6 increasing concentrations of ACh (10⁻¹⁰M to 10⁻¹M) each concentration is perfused for 5 minutes. As SkBF stabilizes with the addition of each concentration of ACh, we proceed to the next concentration. After the last concentration of ACh, we switch perfusates at all sites to Ringer's only for about 30 minutes while increasing the local temperature to 43°C. We add SNP to lactated Ringer's for 10 minutes at each site. Heating and SNP perfusion causes maximum vasodilation.

- b. Then the experiment is over, and we remove the MD tubing from the skin and place sterile bandages over the sites. If the subject desires, we can also place a bag of ice on the site for 10 minutes to reduce any bruising that may occur. We measure blood pressure and heart rate before the subject departs.
3. Subjects take 10 mg/day atorvastatin for 6-9 days. Women who are not postmenopausal undergo a urine pregnancy test before beginning the atorvastatin.
4. Venous blood may be drawn for Chem 24 analysis if a subject experiences side effects from the statin therapy (e.g. dark urine, muscle myalgia).
5. MD Experiment – Post-Statin Therapy
 - a. The subjects return to the lab to repeat the MD experiment within days 6-9 of atorvastatin therapy.
 - b. On the morning of the experiment, the subjects take their final dose of atorvastatin.
 - c. All other preparation and procedures are the same as described for the Pre-statin Therapy MD Experiment.

Equipment:

Laser Doppler Flowmetry: The Laser Doppler Flowmeter (Moor Instruments, Inc.) non-invasively provides a qualitative measure of skin blood flow to a depth of about 1 mm in the skin using a weak laser light. This measure is a dimensionless value called "flux" that reflects the speed and number of blood cells moving through the microvasculature in an area of skin. The flowmeter continuously measures skin blood flow using a fiber optic probe that fits into holders taped to the skin. Approved by the FDA

Blood Pressure, ECG (Heart rate): The critical care monitor measures blood pressure via a cuff inflated every 5-7 minutes on the upper arm and heart rate via 3-lead ECG probes taped to the skin of the chest. Approved by the FDA

12-lead ECG: The critical care monitor measures standard 12-lead ECG during screening via electrodes taped to the skin. Approved by the FDA

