2.0 Background

2.1 Scientific Background and Gaps

Describe the scientific background and gaps in current knowledge.

Endometriosis is an estrogen-dependent gynecological disorder associated with considerable chronic pelvic pain, pain during intercourse, and is a major cause of infertility ^{1,2}. This disorder affects 6% - 10% of reproductive age women and can be as high as 35-50% in women experiencing pain or infertility ³⁻⁶. Endometriosis derives from the presence of endometrium-like tissue in sites outside the uterine cavity. While endometriosis is a local inflammatory syndrome, the inflammatory process is systemic ⁷.

Endometriosis is associated with higher risk of hypercholesterolemia and hypertension ⁸. Epidemiologic data demonstrate a clear association between endometriosis, reproductive risk factors, inflammation and cardiovascular (CV) risk ^{5,8-11}.

Endometriosis and Endothelial Dysfunction: Circulating factors including LDL and oxidized LDL are two of many biomarkers of cardiovascular and inflammatory disease of endometriosis^{9,10}. An important signaling mechanism through which circulating LDL and oxLDL act is the lectin-like oxidized LDL receptor (LOX-1). LOX-1 is a ubiquitously expressed scavenger receptor, stimulated by oxLDL, Ang II, and other inflammatory cytokines, and inhibited by estrogen¹². LOX-1 is the upstream signaling initiator of mechanisms including increased oxidant production, reduced nitric oxide (NO) metabolism, and impaired intracellular trafficking¹³. Thus, LOX-1 signal transduction functionally results in pronounced endothelial dysfunction.

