3.1 Inclusion Criteria

List the criteria that define who will be included in your study.

- Healthy women between the ages of 18 and 45 years (Controls), taking oral contraceptive or with regular menses every 26-34 days
- Women between the ages of 18 and 45 years with endometriosis (diagnosis by prior laparoscopy by subject's own physician, and reported by the subject to the researchers)
- Tylenol if the subject has acute pain is allowed
- Contraceptive use is allowed

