8.3 Statistical methods

Describe the statistical methods (or non-statistical methods of analysis) that will be employed.

Descriptive statistics will be calculated and the variance will be noted for a full power analysis. If appropriate, three-way repeated measures ANOVA (ANCOVAs) will be performed to examine group differences (healthy control vs. endometriosis) or systemic treatment differences (pre-treatment vs. post-treatment), and local microdialysis treatment differences across the doses of pharmacological stimuli with the primary outcome variable of cutaneous vascular conductance. Appropriate post-hoc analyses with corrections for multiple comparisons will be performed when main effects are identified, in all cases including potential confounding variables as covariates.

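### The oral-statin effect is read from an uncontrolled pre/post change, but cycle or pill day is neither controlled nor recorded at either visit and the interval between visits is not stated

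*Combined protocol and SAP*

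**What the plan says.** Section 7.1 has every woman, control or endometriosis, complete one microdialysis experiment before and one after oral atorvastatin. Sections 7.4.3 and 7.4.5 mark assignment to treatment groups and blinding as not applicable, and no no-statin comparison is described. Section 8.3 then examines, among other effects, "systemic treatment differences (pre-treatment vs. post-treatment", with conductance as the primary outcome.

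On timing, 7.2.2 says "Subjects take 10 mg/day atorvastatin for 6-9 days" and "The subjects return to the lab to repeat the MD experiment within days 6-9 of atorvastatin therapy". Both statements count from the start of therapy. The only step that 7.2.2 places before the first tablet is a safety test: "Women who are not postmenopausal undergo a urine pregnancy test before beginning the atorvastatin". The number of days from the pre-statin visit to the first tablet is not given.

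On hormonal status, 3.1 admits controls "taking oral contraceptive or with regular menses every 26-34 days". The other group is defined as "Women between the ages of 18 and 45 years with endometriosis (diagnosis by prior laparoscopy by subject's own physician", with no cycle criterion. For all women, "Contraceptive use is allowed".

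On the biology, 2.1 describes LOX-1 as stimulated by oxLDL, Ang II "and other inflammatory cytokines, and inhibited by estrogen". Soluble LOX receptor is a secondary endpoint (1.3).

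**The concern.** With one fixed order and no untreated comparison, anything that changes within a woman between the two visits is read as atorvastatin. By the protocol's own account, estrogen acts on the receptor under study. In a cycling woman, a gap of about a week is a sizeable part of a cycle. In a user of a cyclic pill, it can move her into or out of the hormone-free week.

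Neither 7.2.1 nor 7.2.2 schedules visits by cycle or pill day, records that day, or names a sex-hormone assay (the blood-draw lists are open-ended, so an assay is not ruled out). The clause in 8.3 on potential confounders as covariates therefore has nothing on this point to work with.

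Two things are at stake. One is how to read the only contrast that addresses systemic LOX inhibition, which 2.3 gives as the reason for the oral statin. The other is the variance that 8.3 says will feed the full power analysis.

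**Working it through.** The plan states no figure for the interval, the phase shift or the hormonal effect, so there is nothing of its own to reproduce.

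**Inputs from the documents:** atorvastatin for 6-9 days with the post visit on therapy days 6-9 (7.2.2); cycle length 26-34 days, for controls not on an oral contraceptive (3.1); 6 completers (8.1).

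**Assumed:** the lag from the pre visit to the first tablet; a 21/7 pill pack; a 14-day second half of the cycle; first visits timed at random.

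**1. Gap between visits.** With the first tablet *lag* days after the pre visit, gap = lag + 5 to lag + 8.
- Tablet on the visit day (lag 0): 5-8 days.
- Tablet the next day (lag 1): 6-9 days.

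**2. Share of a cycle = gap / cycle length.**
- Gap 6-9: 6/34 = 17.6% to 9/26 = 34.6%.
- Gap 5-8: 5/34 = 14.7% to 8/26 = 30.8%.
- Lag 7 (gap 12-15): displacement of 35% to 50%.
- Lag 20-21 (gap 25-29): displacement from 0% up to about 24-27%, so the visits can fall back in phase.

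**3. Visits in different halves of the cycle.** For gaps shorter than either half, P = 2 x gap / length.
- Gap 6-9: 12/34 = 35% to 18/26 = 69%.
- Gap 5-8: 10/34 = 29% to 16/26 = 62%.

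**4. Exactly one visit in the hormone-free week of a 21/7 pack.** P = 2 x min(gap, 7) / 28.
- Gap 5: 10/28 = 36%. Gap 6: 12/28 = 43%. Gaps 7-9: 14/28 = 50%.
- If all six completers used such a pill, that is 6 x 0.36 = 2.1 to 6 x 0.50 = 3 women.

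**5. Variance or bias.** Suppose, for illustration, a sinusoidal phase effect of unknown amplitude A, and let f be the share of a cycle between visits. The largest shift in one woman is 2 sin(pi f) A. With random starting phase the mean shift is 0, the SD in one woman is that maximum divided by sqrt(2), and the SD of the mean of six divides again by sqrt(6).

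| f | Largest shift | SD, one woman | SD, mean of 6 |
|---|---|---|---|
| 5/34 | 0.89A | 0.63A | 0.26A |
| 6/34 | 1.05A | 0.74A | 0.30A |
| 9/26 | 1.77A | 1.25A | 0.51A |

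Random timing therefore adds between 0.63² = 0.40 and 1.25² = 1.57 times A² to the variance of the pre/post change, without moving its expected value. If all women started at a similar phase, the scatter would become a common shift of up to the second column. A is not in the documents.

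**The case against.** The strongest reply has four parts.

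- **Unlinked starting phases give no expected bias.** This stands. The problem is added scatter. With six women, though, random phases need not balance, and the SD of their mean remains 0.26A to 0.51A.
- **If the full study keeps the same schedule, an SD that includes phase scatter is the right planning input.** This also stands. But the scatter can be partly avoided, and without a record of cycle or pill day nobody can say how much of it is hormonal or whether a tighter schedule would pay.
- **This is a six-woman pilot, declared open to modification, with ANOVA only if appropriate; no hypothesis in 1.1 names the pre/post contrast, and probe contrasts within one visit are untouched.** All true, and it limits the weight of the point. Still, those within-visit contrasts test local inhibition, and the pilot is the cheapest stage at which to add the record.
- **Section 8.3 already allows confounders as covariates.** It does, but this one is neither named nor collected.

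A reader might go further and infer that every cycling woman moves 18-35% of a cycle, that the protocol says cycle phase alters LOX-1, or that the primary endpoint is biased. The documents do not support these. The 6-9 days is the length of treatment, not the stated interval. The 26-34 day range covers only controls not on an oral contraceptive. Section 2.1 speaks of estrogen, not phase. No effect on conductance is given: the nearest pointer is the title of one cited study, on progestin and skin responses to passive heating, which supplies no figure here.

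**Conclusion.** The point holds as a gap in control and recording. In naturally cycling women and in users of cyclic pills, the pre/post change in soluble LOX-1, and possibly in conductance, cannot be separated from hormonal change.

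The size of the displacement depends on the unstated lag. It is about 18-35% of a 26-34 day cycle if the first tablet follows the visit by a day, and about 15-31% if it is taken on the visit day. With an assumed 21/7 pack and a gap of 5-9 days, 36-50% of users would have mismatched visits. No range can be given for women with endometriosis who cycle outside 26-34 days.

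The main consequence is extra variance, which matters with 6 completers and because the variance is carried into the power analysis. It becomes bias only if starting phases cluster, and nothing in the documents shows that they do. How much either matters depends on a hormonal effect whose size the documents do not give. This is a cheap improvement to the plan, not a reason to set the pilot's results aside.

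**What to change.** **In 7.2.2**, leaving the atorvastatin course unchanged:
- State the interval between the two visits, including the days from the pre-statin visit to the first tablet.
- For oral-contraceptive users, choose the pre-statin date so that both visits fall on hormone-containing pill days.
- At both visits, record cycle day (from last menses) or pill day, and contraceptive type, for all women including those with endometriosis.

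**In 8.3**, report the pre/post change separately for women whose visits fell in the same and in different hormonal windows, and name this as the covariate. With six completers the split can only be descriptive; the covariate earns its place in the full study.

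Two tempting rules should be avoided. Timing all first visits to one cycle window would put every second visit about a week later, turning scatter into a shift in one direction. Requiring both visits in the same half-cycle does much the same. In a 26-day cycle the first half is 26 - 14 = 12 days, so a 9-day gap forces the first visit onto days 1-3 and the second onto days 10-12. Counting from last menses cannot place the boundary either, since under the same assumption the first half runs from 12 to 34 - 14 = 20 days.

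**Cost:** a short recorded item per visit and some waiting for pill users. With a 21/7 pack and a 9-day gap, the first visit can fall on 21 - 9 = 12 of 28 days, so the longest wait is 28 - 12 = 16 days. Drift in cycling women remains, but it becomes visible.
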